10.3. Other covariates

Patient characteristics may influence the TTP dynamics, like the severity of disease at start of treatment (degree of cavitation, baseline bacterial load), co-infection with HIV, sex, adherence to treatment, etc. Those factors will be evaluated as predictors for the decline in bacterial load. Likelihood ratio tests and a 5%-significance level will be used for testing the statistical significance of inclusion of covariate effects.

Parameter estimates with corresponding uncertainty for the final model will be reported.

11. Outcome Definitions

11.1. Culture results

Two sputum specimens at each visit for culture. The culture results are reported as:

- Positive for MTB Complex
- Positive for MTB Complex with contamination
- Negative
- Contaminated

No result

With the potential for results from two sputum samples at each time-point(visit) a rule is required to define a negative or a positive time-point for determination of sputum-culture conversion. For this trial the definitions are:

- **Positive timepoint** Any timepoint with one or more culture result of Positive for MTB Complex or Positive for MTB Complex with contamination
- Negative timepoint Any timepoint with one or more culture result of Negative and no cultures with a result of Positive
 for MTB Complex or Positive for MTB Complex with contamination
- Contaminated timepoint Any timepoint with one or more culture result of Contaminated and no cultures with a result of Positive for MTB Complex or Positive for MTB Complex with contamination or Negative
- No result timepoint Any timepoints with no positive, negative, or contaminated results reported for any specimen submitted for analysis

11.2. Relapse

An important secondary outcome is the proportion of participants who suffer relapse among those completing 16 weeks of therapy, achieve early culture conversion to negative in liquid media if there is a culture negative timepoint at two consecutive visits, the first of which is at or before week 08, without an intervening culture positive timepoint, and terminating therapy.

All participants will be classified as follows:

- Not achieved culture conversion to negative before or at week 8 after randomization (based on the analysis visit window).
 These participants will not end treatment at week 16 according to the protocol and therefore are not included in the relapse analysis.
- Relapse defined as having two consecutive culture positive timepoints without an intervening culture negative timepoint where the first occurs after Week 16 after randomization (based on the analysis visit window) and the recurrence strain of MTb is shown to be the same as that at baseline. If strain typing results are missing or inconclusive, a recurrence will be considered a relapse (rather than a reinfection).
- Reinfection defined as having two consecutive culture positive timepoints without an intervening culture negative timepoint where the first occurs after Week 16 after randomization (based on the analysis visit window) and the recurrence strain of MTb is shown to be different from that at baseline.
- Died at any point during the study
- Culture positive timepoint when last seen (not meeting criteria for other outcomes above)
- Culture negative timepoint when last seen (not meeting criteria for other outcomes above)

Outcomes will be tabulated by treatment arm among all in the ITT analysis population and among those in the AA analysis population.

A sensitivity analysis will be conducted repeating this relapse analysis using the second definition of time to culture conversion described below under the latter part of section 11.4.

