#### 9.2.2 Secondary Efficacy Endpoints

Further efficacy of DZD will be evaluated by assessment of:

- Proportion of patients who suffer relapse, defined as recurrent disease caused by a strain identical to the baseline isolate, within 12 months post randomisation, out of patients completing 16 weeks of therapy and achieving stable culture conversion to negative (SCC) as defined below by week 08, with no positives to follow by the week 16 visit.
- Time to recurrent TB, and to relapse, within 12 months post randomisation
- Time to stable sputum culture conversion (SCC) to negative on liquid media (defined as two negative cultures without an intervening positive culture). Time will be measured as time on treatment until the first negative culture.
- Proportion of participants who achieved SCC at each time point during treatment
- Proportion of participants with negative sputum culture on solid media at WK 08 and other timepoints
- Proportion of participants developing drug resistance among those not converting to negative culture

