# 12.4 Treatment after End of Study Therapy (Post-study Access to Treatment)

The strategy recommended for participants to continue their TB treatment within the government health system is informed by two previous phase 2b TB trials with a 2-month experimental treatment, and the solution found for patients in Tanzania in collaboration with the national TB program in those past trials [27, 56, 59].

Patients who achieve two successive negative liquid media cultures, with no positives to follow by WK16 visit, the first of which is at or before WK 08, will NOT receive standard of care TB-treatment according to national guidelines as continuation phase to complete 6 months of treatment. Their planned post-treatment follow-up visits at WK 18, WK26, WK38 and WK52 will serve to determine

whether they have achieved lasting cure. Patients who will NOT fulfil at least one of these criteria will receive standard of care TB-treatment according to national guidelines until WK26 at a government health facility (continuation Phase).

They will be invited to return to the WK52 follow-up visit to determine their wellbeing and treatment outcome.

The review of culture results, and decision to discontinue or continue treatment will be made on the day before the WK16 visit. Should sufficient culture results to take this decision not be available by this timepoint, but available culture results indicate good response to treatment in the view of the investigator, this decision, and the start of continuation phase treatment, may be delayed until latest to WK16 (day112) + 6 days.

Should positive results become available after a decision is taken to discontinue treatment after WK16, the investigator should discuss these with the sponsor medical expert to come to a conclusion of whether the management of the patient should be changed, which should be done only in exceptions.

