5.2.2. Secondary Efficacy Endpoints

- Proportion of participants who suffer relapse, defined as recurrent disease caused by a strain indistinguishable to the baseline isolate (using whole genome sequencing), within 12 months post randomization, out of participants completing 16 weeks of therapy and achieving sustained sputum culture conversion defined as two successive negative liquid media cultures at or before WK08, with no positives to follow by the week 16 visit. Full definition of relapse in section 11.2.
- Time to recurrent TB, and to relapse, within 12 months post randomization.
- Time to culture conversion to negative on liquid media (defined as two negative cultures without an intervening positive culture).
- Proportion of participants converting to negative sputum culture in liquid media (defined as two negative cultures
 without an intervening positive culture) at each time point during treatment.
- Proportion of participants with negative sputum culture on solid media at WK 08 and other time-points.
- Proportion of participants developing drug resistance among those not converting to negative culture.

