11.4. Time to culture conversion to negative on liquid media

Participants will be classified as having culture conversion to negative in liquid media if there are two consecutive culture negative timepoints without an intervening culture positive timepoint. Any other results will be ignored for the calculation of time to culture conversion. Culture timepoints will be classified as negative or positive according to the trial definition under 11.1.

Time will be taken from the date of randomization to the first occurrence of two consecutive negative culture timepoints.

Culture positive timepoints that occur after culture conversion has been achieved do not affect time to culture conversion.

This will be the primary definition of time to culture conversion. Primary analysis will be performed based on the primary definition. We will, in addition, perform two sensitivity analyses with alternative definitions of time to culture conversion:

- 1) The definition will be as above, with the exception that culture conversion can only be achieved if the two consecutive visits assessed as culture negative timepoints without an intervening culture positive timepoint are at least 28 days apart.
- 2) The definition will be as above, with the exception that culture conversion is only achieved provided no further culture positive timepoints occur after 'culture conversion', in the period up to and including the week 16 visits (a subsequent culture positive timepoint effectively 'cancels' out culture conversion).

12. Analysis Method

12.1. Analysis of time to culture conversion by dose group.

Descriptive summary statistics, such as mean/median of the time to culture conversion will be tabulated. Proportion of participants achieving culture conversion at each time point during treatment will be summarized using the Kaplan-Meier estimator with 95% confidence intervals.

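### SAP 11.2 names one relapse population in its lead sentence and applies a wider one in its list: only participants not converted by week 8 are removed, and the no-later-positive condition is explicit only in the sensitivity analysis

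*SAP*

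**What the plan says.** **Endpoint.** SAP 5.2.2 takes relapse out of participants who complete 16 weeks and have "two successive negative liquid media cultures at or before WK08, with no positives to follow by the week 16 visit". Protocol 9.2.2 has the same condition on later cultures: "with no positives to follow by the week 16 visit". SAP 5.2.2 points to 11.2 for the full definition of relapse.

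**Lead sentence of SAP 11.2.** The outcome concerns participants completing 16 weeks with two consecutive negative visits, "the first of which is at or before week 08, without an intervening culture positive timepoint, and terminating therapy".

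**Classification list of SAP 11.2.** Everyone is to be classified. The only exclusion is failure to convert by week 8, with the reason "These participants will not end treatment at week 16 according to the protocol and therefore are not included in the relapse analysis". The other classes are relapse, reinfection, death, and culture positive or negative when last seen. The Table 2.10 shell has the same rows, under the ITT total, and states no relapse denominator.

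**Conversion in SAP 11.4.** Under the main definition, "Culture positive timepoints that occur after culture conversion has been achieved do not affect time to culture conversion". Under alternative definition 2, "culture conversion is only achieved provided no further culture positive timepoints occur after" conversion, through the week 16 visits. SAP 11.2 then adds: "A sensitivity analysis will be conducted repeating this relapse analysis using the second definition of time to culture conversion".

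**Stopping therapy.** The protocol synopsis and 12.4, and SAP 4.1, require no later positive before therapy is stopped; otherwise the participant is referred for further treatment. Protocol 12.4 also foresees late results: "Should positive results become available after a decision is taken to discontinue treatment after WK16", the case goes to the sponsor medical expert, and management changes only exceptionally.

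**The concern.** The list's reason for excluding non-converters is that they continue treatment. That reason applies equally to a converter with a known later positive, yet the list keeps that participant. Someone who converted but did not complete or stop therapy is also kept.

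At stake is what the main relapse proportion means. The SAP calls relapse an important secondary outcome, and it is the plan's evidence on whether 16 weeks is enough for early converters. Participants on further standard treatment are not at risk of relapse after a 16-week regimen in the same sense, and they are cultured less often. If they are counted in, the tabulated proportion is not the one the endpoint describes, and a reader of Table 2.10 could not tell.

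**Working it through.** The documents give no expected relapse rate and no sample size for relapse, so there is no planned figure to reproduce. The check compares the passages, then counts visits.

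**1. Which condition is applied where**

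| Condition | SAP 5.2.2, protocol 9.2.2 | 11.2 lead sentence | 11.2 list (main) | 11.2 sensitivity analysis |
|---|---|---|---|---|
| Completed 16 weeks | yes | yes | no | no |
| Converted by week 8 | yes | yes | yes | yes |
| No positive up to week 16 | yes | only indirectly, through the stop rule | no | yes |
| Stopped therapy | not stated | yes | only as a reason for the exclusion | no |

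**2. Test histories** (11.4 main definition against alternative 2, first negative by week 8)

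- Negative at weeks 6 to 16: in both sets.
- Negative at weeks 6 and 7, positive at week 12, then negative: in the main set, out of the sensitivity set. With the week 12 result known, this participant does not stop therapy, and does not meet 5.2.2.
- First negative at week 9: in neither set.

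**3. Room for a later positive.** There are weekly visits to week 16 with two MGIT cultures each. Negatives at weeks 8 and 9 leave weeks 10 to 16: 7 visits × 2 = 14 cultures. Negatives at weeks 1 and 2 leave weeks 3 to 16: 14 visits × 2 = 28 cultures. These are opportunities, not expected events.

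**4. Follow-up** (protocol section 2 note A, and 10.5.3). Participants who stop have weeks 18, 26, 38 and 52: 4 timepoints. Those referred for further treatment have weeks 18 and 52: 2 timepoints, 52 − 18 = 34 weeks apart. Relapse needs two consecutive positive timepoints, so on scheduled visits the second group must be positive at both.

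**5. Late-reported positives.** Visit w falls on day 7w. The stop decision is on day 111, or at the latest on day 112 + 6 = 118. The documents give no reporting lag; assume 14, 28 or 42 days. A collected culture is pending if 7w + lag exceeds the decision day.

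- Day 111: weeks 14–15 (2 visits), 12–15 (4) or 10–15 (6). The week 16 sample, due on day 112, has not yet been collected.
- Day 118: weeks 15–16 (2 visits), 13–16 (4) or 11–16 (6).

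A participant can therefore stop therapy and still break the 5.2.2 condition.

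**6. Effect on the proportion** (assumed counts, for illustration only). Take an arm of 15 with 12 converters, m of whom had a later positive and did not stop, and 2 relapses among those who stopped.

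- List as written, with none of the m classed as relapse: 2/12 = 16.7% for any m.
- Stated endpoint, 2/(12 − m): 18.2% (m = 1), 20.0% (m = 2), 22.2% (m = 3), 25.0% (m = 4).
- If m = 2 and one of the two is classed as relapse, the list gives 3/12 = 25.0% against 2/10 = 20.0%.
- If Table 2.10 percentages are taken on all ITT participants: 2/15 = 13.3%.

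At m = 0 the list and the endpoint agree.

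**The case against.** The strongest reply is that the lead sentence of 11.2 already settles the matter. It confines the outcome to participants who complete 16 weeks and terminate therapy, and the SAP is to be read with the protocol, under which a known later positive bars stopping. The lead sentence thus brings in most of the 5.2.2 condition. That stands, and it limits what can be claimed:

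- A reader might infer that the SAP has reversed its main and sensitivity analyses. The documents do not show that; they show a lead sentence and a list that disagree.
- A reader might infer that the main tabulation misses the endpoint however 11.2 is read. If the lead sentence governs, the sets differ only for participants who stopped before a late-reported positive, and they coincide if there are none. The endpoint could even be read as meaning results known at the decision, although definition 2 in 11.4 works on culture timepoints and not on reporting dates.
- A reader might infer that converters who did not stop cannot be classified. They can, because the last-seen classes are residual. They are misplaced and lack a label and a denominator of their own.

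The reply does not remove the conflict. The list is the operative text, its exclusion line draws a different boundary, and the table shell follows the list. It is also fair that relapse is secondary, that 11.2 plans only a tabulation by arm, and that a figure close to the endpoint would appear in the sensitivity analysis.

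**Conclusion.** The point holds as an internal conflict in SAP 11.2, and between its list and the endpoint in SAP 5.2.2 and protocol 9.2.2. As listed, the main relapse set keeps converters with a later positive and converters who did not complete or stop therapy. It should be corrected, but it concerns a descriptive secondary endpoint.

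The number affected, and the size and direction of the effect, cannot be derived from the documents; the percentages above rest on assumed counts and the pending-culture ranges on an assumed lag. The conclusion also assumes that the second definition cited in 11.2 is item 2 of 11.4. That is the natural reading, but the SAP does not name the item, and the phrase could be taken to mean the 28-day definition.

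A reader might think that exchanging the two analyses is enough. It is not, because neither applies completion or actual stopping. Two neighbouring questions are separate clarifications and not part of this point: whether cultures from a suspected-recurrence work-up form their own timepoint, and how the unblinding in SAP 13.4 fits with protocol 13.6.

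**What to change.** 1. In SAP 11.2, define the main relapse set as participants who completed 16 weeks, met alternative definition 2 of 11.4 (named by number) with the first negative at or before week 8, and actually stopped therapy.
2. Add separate rows in 11.2 and Table 2.10 for converters with a later positive and for converters who did not complete or did not stop therapy. State the relapse denominator in the table.
3. Show participants who stopped before a late-reported positive in their own row, and include them in a sensitivity analysis of all who actually stopped.
4. Align the timing wording. SAP 3.2.2 and 5.2.2, and the objectives in protocol sections 1 and 8.1.1, place both negatives by week 8. The operative rule in SAP 11.2 and protocol 12.4 needs only the first by then. Negatives at weeks 8 and 9 meet the operative rule but not the other wording.

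The cost is SAP text, a few table rows, one stated denominator and one more tabulation from data already collected. The protocol wording would go through the amendment route in protocol 18.7. The rule for stopping therapy is untouched. The downside is a smaller main denominator in arms of 15.

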	
 
To assess the minimum inhibitory concentrations (MIC) of BDQ, DLM, MXF, DZD of the infecting strain, at baseline and on representative isolate(s) grown at or after WK08.
 

	
 
To investigate the frequency of acquired mutations in the infecting strain over treatment
 

	• In patients with recurrent disease: comparison of initial and recurrence isolate by whole genome sequencing to discriminate relapse from reinfection
Study Design	This will be an open label Phase IIb dose-finding, randomized, controlled study with a duration of 16 weeks of experimental therapy of DZD – Bedaquiline/Delamanid/ Moxifloxacin (BDM) in adult patients with newly diagnosed, smear positive, uncomplicated, drug sensitive pulmonary tuberculosis (TB) to evaluate the safety, efficacy, tolerability, pharmacokinetics and exposure/response-relationship of different doses of delpazolid in combination with bedaquiline, delamanid and moxifloxacin.
	Participants will be randomized to one of five arms containing BDM with different doses of DZD:
	
 
Arm 1 (D0): 15 patients will receive 0 mg of DZD
 
Arm 2 (D400): 15 patients will receive 400 mg DZD orally once daily
 
Arm 3 (D800-OD): 15 patients will receive 800 mg DZD orally once daily
 
Arm 4 (D1200): 15 patients will receive 1200 mg DZD orally once daily
 
Arm 5 (D800-BD): 15 patients will receive 800 mg DZD orally twice daily
 

Decision rule for managing post week 16 treatment or follow - up	Patients will stop therapy after the week 16 visit, if they achieve early sputum culture conversion (SCC) to negative. This is defined as two successive negative liquid media cultures, the first of which is at or before week 08, with no positive cultures to follow.
	Results for the negative cultures need to be available by the week 16 (day 112) visit, with a time window of +6 days to accommodate for late availability of culture results, in order for patients to stop therapy.
	Post treatment follow-up visits at weeks 18, 26, 38 and 52 will serve to determine whether they have achieved lasting cure. Patients with a positive culture or other indication as described under 11.4 during the follow up period will undergo a standardized assessment for potential poor treatment outcome. If this procedure results in a diagnosis of recurrent disease, they will be referred to the national TB program.

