Protocol No: PanACEA - DECODE – 01/ LCB01-0371-20-2-02 Protocol Version No: V2.1, dated 08 September 2021

- A) Continuation Treatment and follow-up visits: Participants of all 5 arms will complete their experimental treatment on Day 112. Omission of anti-TB treatment after this and conduct of follow-up visits 2-3 will be conditional on culture conversion with first negative at or before WK08 (see decision rule). Participants who do not convert to negative culture will receive standard TB treatment according to their national TB program through governmental clinics, and will not have visits FU 2 and FU3. FU 4 will be conducted for all participants.
- B) Serum pregnancy test: blood samples of 7.5mL; for women of childbearing potential only.
- C) HIV Testing: blood samples of 7.5mL will be taken; CD4 count if HIV positive. If the patient is on ARVs at the time of screening, perform viral load count. Genotypic resistance testing mandatory if viral load is insufficiently controlled (>1,000 copies/μl) and patient would need to be switched back to a non-dolutegravir regimen after the study, recommended otherwise.
- D) Urine drug screening: for opiates, amphetamines, cannabinoids, cocaine, benzodiazepines and barbiturates. Results on other drugs generated by a combination test may be used as well.
- E) Sputum sampling: 3 sputa will be collected per time point during treatment phase, 1 spot sputum at SCR and 2 at FU 1-4 each. Two spot sputum samples during treatment and follow-up phase will be processed for mycobacterial culture MGIT liquid culture at all time-points. LJ will be performed at WK00, WK08, WK12, WK16, and FU1-FU4 from two samples each. An isolate from baseline, and all isolates from all cultures positive after WK08 will be stored. The third sputum sample may be a spot or an early morning sputum, and will be stored for future biomarkers work. A Ziehl-Neelsen stained sputum smear will be performed at SCR and WK16 from concentrated sputum and at additional visits as required by the national TB programs.
- F) Physical examination and vital signs: Additional Blood pressure and heart rate recordings WK00 at 1h, 2h and 3h (± 10 mins) after intake of IMP and WK02 during hospitalization at 1h, 2h, 3h, 4h, 6h (± 10 mins) after intake of IMP with a meal. During follow up visits FU 2-4 symptom orientated physical examination only or to follow up on (S)AEs.

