#### **10.2** Trial population

Participants will be randomized to one of five arms containing a BDM backbone with different doses of DZD, ranging from 0mg DZD (no DZD present in the regimen) up to 1,600mg (800mg BD). 75 participants will be randomized into this study, with 15 participants per arm.

In the case of unforeseen delays or a rate of dropouts or non-evaluable participants that is higher than anticipated, it may be necessary to recruit more participants than planned into the entire study (see sample size considerations, Chap. 15.1).

Participants will be randomised by centralized allocation, using a probabilistic minimisation algorithm, which will stratify participants by bacterial load in sputum as measured by GeneXpert cycle threshold, site and HIV status.

Participants will visit the study clinic on a weekly basis for sputum collection, safety monitoring and receipt of study medication.

After the completion of 16 weeks of experimental treatment, participants in the experimental arms, who did not achieve two successive negative liquid media cultures with the first at or before WK08, with no positives to follow by the week 16 visit, will be referred to their local health care facility to complete their course of anti-TB treatment according to the national TB program.

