#### 10.5.3 Follow-up Period

#### Visits FU 1 at WK18 (Day 126 ±4 days): all patients

FU 2,3 at WK26, WK38 (Day 182, Day 266, each ±7 days): only patients with sputum culture conversion who end treatment after week 16.

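### SAP 11.2 sets aside only participants not converted by week 8, so the main relapse analysis omits the endpoint's own condition of no positive cultures up to week 16

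*SAP*

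**What the plan says.** **Stopping rule.** The protocol synopsis lets a participant stop after week 16 on "two successive negative liquid media cultures, the first of which is at or before week 08, with no positive cultures to follow". Protocol 10.2 covers those who do not reach two successive negatives "with no positives to follow by the week 16 visit, will be referred to their local health care facility". SAP 4.1 repeats this. Under Protocol 12.4 they "will receive standard of care TB-treatment according to national guidelines until WK26 at a government health facility".

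**Endpoint.** SAP 5.2.2 defines the relapse denominator as participants who completed 16 weeks and converted by week 8, "with no positives to follow by the week 16 visit". Protocol 9.2.2 has the same condition.

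**Classification.** The lead sentence of SAP 11.2 limits the outcome to those who completed 16 weeks, converted early and ended therapy. The list that follows assigns every participant to one of six classes. The only class set aside is non-conversion by week 8, with the reason: "These participants will not end treatment at week 16 according to the protocol and therefore are not included in the relapse analysis".

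**Conversion.** Under the primary definition in SAP 11.4, "Culture positive timepoints that occur after culture conversion has been achieved do not affect time to culture conversion". Its second alternative definition cancels conversion if a positive follows up to and including week 16. SAP 11.2 repeats the relapse analysis with that definition as a sensitivity analysis.

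**Follow-up.** Participants who go on to standard treatment "will not have visits FU 2 and FU3" (Schedule of Events, footnote A). Protocol 10.5.3 reserves those two visits for "only patients with sputum culture conversion who end treatment after week 16". The week 18 and week 52 visits are for everyone.

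**The concern.** The relapse outcome asks how often disease returns once treatment ends at 16 weeks. A participant who converts at week 6 and is positive at week 12 does not satisfy the stopping rule and would normally be treated to about week 26. The reason SAP 11.2 gives for setting non-converters aside applies equally to this participant, but the class list does not set them aside. They are counted as relapse, reinfection, death, or culture-positive or culture-negative at last observation, together with those who stopped.

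Three things are at stake. The main result does not describe the population in SAP 5.2.2. The two-consecutive-positives rule is applied to people with a different visit schedule and further treatment. And SAP 11.3 carries those without an event as event-free to their last culture, with no allowance for the extra treatment. Late positives may differ by dose, so the effect need not be the same in every arm.

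**Working it through.** The plan gives no figure to reproduce here, so the check applies the written rules to example histories and then gives conditional sizes.

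**1. The rules applied to four histories**

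| History | Main rule (SAP 11.2 with the SAP 11.4 primary definition) | Second definition |
|---|---|---|
| A: converts week 6, negative throughout to week 52 | Culture-negative at last observation | Same |
| B: converts week 6, positive week 12, negative weeks 18 and 52 | Culture-negative at last observation | Set aside |
| C: converts week 6, positive weeks 12, 18 and 52 | Relapse, or reinfection if the strain differs | Set aside |
| D: converts week 11, negative weeks 18 and 52 | Set aside | Set aside |

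B and C fail the stopping rule and the SAP 5.2.2 denominator, yet the main rule keeps both. In C, SAP 11.3 dates the event to week 18, when the participant would be on standard treatment.

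**2. Follow-up from scheduled visits**

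Days from the Schedule of Events: week 16 = 112, week 18 = 126, week 26 = 182, week 38 = 266, week 52 = 364.

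- A participant who stops has 4 visits after week 16 (18, 26, 38, 52), giving 3 consecutive pairs wholly off treatment.
- One who continues to week 26 has 2 (18 and 52). The single pair starts on treatment, so no pair lies wholly after treatment.
- Share of the period from week 16 to week 52 spent on standard treatment: (182 − 112)/(364 − 112) = 70/252 = 27.8%.

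On scheduled visits alone, a relapse after week 26 in someone who continued cannot meet the two-positive rule.

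**3. Effect on a proportion among converters**

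Assumed, not from the documents: 12 of 15 in an arm convert by week 8, k of them are positive again by week 16, and all relapses occur among those who stopped. The main rule uses 12 as the denominator; the endpoint uses 12 − k.

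| k | 2 relapses, endpoint denominator | 2 relapses, main rule |
|---|---|---|
| 0 | 2/12 = 16.7% | 16.7% |
| 1 | 2/11 = 18.2% | 16.7% |
| 2 | 2/10 = 20.0% | 16.7% |
| 3 | 2/9 = 22.2% | 16.7% |
| 4 | 2/8 = 25.0% | 16.7% |

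With 1 relapse, the main rule gives 8.3% and the endpoint denominator 8.3% to 12.5% over the same range of k.

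**4. How common late positives must be to matter**

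No reversion rate is given in the documents. Suppose n converters in an arm each have m visits after conversion, with the same independent chance p of a positive timepoint at each visit. One affected participant is expected when n[1 − (1 − p)^m] = 1, that is p = 1 − (1 − 1/n)^(1/m).

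- n = 10, m = 7 (weeks 10 to 16): p = 1.49%
- n = 12, m = 7: p = 1.24%
- n = 5, m = 7: p = 3.14%
- n = 10, m = 4: p = 2.60%

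These are thresholds, not estimates of the rate.

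**The case against.** The strongest reply is that SAP 11.2 already deals with this. Its lead sentence requires that therapy was ended, and its last sentence repeats the analysis under the definition that removes histories B and C. This stands in part: what remains is which result is primary. But the lead sentence has no counterpart in the class list that would be programmed, and the roles are reversed relative to SAP 5.2.2. A reader might infer that 11.2 ignores the stopping condition altogether; the lead sentence and the sensitivity analysis rule that out.

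A reader might also infer that the reported relapse percentage is bound to be diluted. The documents do not support this. Table 2.10 is headed by the ITT total. If its percentages use that total, step 3 does not apply there and only histories like C change the relapse figure. The cost then is that the endpoint's own denominator is not shown.

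The Table 2.10 row for participants without stable conversion might be meant to catch these cases. The synopsis decision rule supports that reading; the endpoint list in Protocol 9.2.2, which defines stable conversion without the later-positive condition, does not. The row is ambiguous, and the shells may be updated.

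Nor does every participant with a later positive continue treatment. Protocol 12.4 says that positives arriving after the decision to stop should change management only exceptionally, so some will have stopped.

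Finally, Protocol 11.4 calls for a standardised assessment with three further sputum specimens after any confirmed positive at or after week 16, and does not limit this to those who stopped. That can supply cultures missing from the schedule. A participant who stopped and is first positive at week 52 also needs a further culture. The follow-up imbalance is therefore one of scheduled visits, not a bar to detecting relapse.

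**Conclusion.** The point holds as an internal inconsistency. The class list in SAP 11.2, read with the primary definition in SAP 11.4, conflicts with the lead sentence of 11.2, with SAP 4.1 and 5.2.2, and with the protocol's stopping rule. The condition of no positives up to week 16 is applied only in the sensitivity analysis.

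This follows from the text and needs no assumption. Its size does: the number of affected participants cannot be determined from the documents, and the percentages in step 3 depend on assumed counts and on converters being the denominator. With 15 per arm, one or two participants would be visible in the result. The consequence is confined to relapse and time to recurrence or relapse, which are secondary, and no between-arm test of relapse is specified. The primary endpoints are unaffected. The correction should be made before the final analysis.

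**What to change.** 1. In SAP 11.2 and 11.3, define the primary relapse set by the second alternative definition in SAP 11.4 (a later positive up to and including week 16 cancels conversion), together with completion of 16 weeks. Move the current rule to the sensitivity analysis.
2. Add a class to 11.2, and a row to Table 2.10, for participants who converted by week 8 and had a later positive by week 16.
3. In Table 2.10, report relapse with the SAP 5.2.2 denominator beside the ITT counts.
4. List participants whose actual week 16 treatment decision disagrees with their culture class. The actual decision should not replace the culture-based denominator: the endpoint is defined by completion and cultures, and Protocol 12.4 leaves room for investigator judgement in an open-label trial.
5. Keep the SAP 11.4 primary definition for time to conversion.

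The cost is SAP text, one table row, one added denominator and one listing. The culture data are already collected, and no protocol amendment, visit or sample is needed. The listing depends on the week 16 decision having been recorded, which cannot be seen from these documents. The relapse denominator may fall slightly.
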